## 4 Trial population

#### 4.1 Screening data

Screening data will be reported and described within a CONSORT flowchart.

#### 4.2 Eligibility

The eligibility criteria are listed in Table 4. All inclusion criteria must be fulfilled. If at least one of the exclusion criteria is met, patients are excluded. Informed consent needs to be signed prior to enrolment to the study.

Table 4 Eligibility criteria

Inclusion criteria:	Exclusion criteria:		
Clinical diagnosis of idiopathic PD according to the MDS clinical diagnostic criteria for Parkinson's disease.	Dementia or other neurodegenerative disorder at baseline.		
FP-CIT Single-Photon Emission Computed	
 
Diagnosed with atypical or vascular Parkinsonism.
 
		
Tomography Imaging of the Dopamine Transporter confirming nigrostriatal denervation.	Any psychiatric disorder that would interfere with compliance in the study.		
Diagnosed with PD within 2 years from enrolment.	
 
Any severe somatic illness that would make the individual unable to comply and participate in the study.
 
		

Confidential Page 12 of 21

- Hoehn & Yahr Score < 3 at enrolment.

- Optimal symptomatic therapy, not requiring adjustments, for at least 1 month.
- Age ≥35 years at time of enrolment.
- Use of high dose vitamin B3 supplementation within 30 days of enrolment.
- Metabolic, neoplastic, or other physically or mentally debilitating disorder at baseline.
- Genetically confirmed mitochondrial disease.

#### 4.3 Recruitment

Recruitment numbers will be reported and described within a CONSORT flowchart.

#### 4.4 Withdrawal/follow-up

Reasons for withdrawal will be documented using a CONSORT flowchart. Reasons for drop-out are collected in a corresponding form within the trial data base. Patients who are withdrawn from the study before the start of treatment, will be replaced.

#### 4.5 Baseline patient characteristics

All baseline patient characteristics will be summarized using descriptive statistics (e.g. mean, standard deviation, median, IQR for continuous variables and frequencies (percentages) for categorical variables) and appropriate graphical methods (e.g. boxplots, histograms, barplots) depending on the data type.

# 5 Analysis

#### 5.1 Outcome definitions

Instrument	Description	Missing values
Movement	MDS-UPDRS is a 4-subscale scale assessing clinical impairment	Any missing value
Disorder	and disability in PD. Part IV is not applicable. All items are scored	invalidates the
Society	on a scale from 0 (normal) to 4 (severe).	total score.
Sponsored	Part I: Non-motor experiences of daily living (Range: 0-52).	
Revision of	Part IA has 6 items (R: 0-24) and Part IB 7 items (R: 0-28).	
the Unified	Part II: Motor experiences of daily living (13 items, R: 0-52).	
Parkinson's	Part III evaluates motor severity and contains 33 scores	
Disease	based on 18 items being assessed by a rater (R: 0-132).	
Rating Scale	For all parts the score is the sum of the scored items. The	
(MDS-	total score is the sum of all parts (Range: 0-236).	
UPDRS) [1]	, , ,	
Hoehn & Yahr	Assessed by the Hoehn & Yahr stage in MDS-UPDRS.	
Scale	• Classification: 0 = Asymptomatic, 1 = Unilateral involvement,	
	2 = Bilateral involvement, 3 = Bilateral involvement with	
	postural instability, 4 = Severe disability, 5 = wheelchair	
	bound	
Movement	The diagnosis of clinically established PD requires	
disorder PD	Absence of absolute exclusion criteria	
clinical	At least two supportive criteria	

Confidential Page 13 of 21

diagnosis	3. No red flags	
criteria	Diagnosis of Clinically Probable PD requires:	
(MDSCDCPD)	Absence of absolute exclusion criteria	
[2]	Presence of red flags counterbalanced by supportive	
[4]	criteria.	
	If 1 red flag is present, there must also be at least 1	
	supportive criterion.	
	If 2 red flags, at least 2 supportive criteria are needed.	
	No more than 2 red flags are allowed for this category.	
Non-Motor	30-item scale assessing frequency and severity of non-motor	Any missing value
Symptom	symptoms in PD, covering nine domains: cardiovascular,	invalidates the
assessment	sleep/fatigue, mood/cognition, perceptual problems,	total score.
scale for	attention/memory, gastrointestinal, urinary, sexual function,	total soore.
Parkinson's	and miscellany.	
Disease	Each item is scored based on the severity from 0 to 3 points	
(NMSS) [3]	and frequency from 1 to 4, if severity is ≥1.	
(	The total score ranges from 0 to 360.	
Montreal	30 items questionnaire used for assessing cognition	Any missing value
Cognitive	Score: Sum of points, range 0-30	invalidates the
Assessment	o If the score is <30 and education ≤12 years, an extra	total score.
(MoCA) [4]	point is added.	total soore.
, , , , , , ,	Higher values indicate a healthier state	
EQ-5D-5L [5]	Used to measure QoL	In case of death,
	• 5 items scored 1-5 and a visual analogue scale (EQ-VAS,	the index value is
	range 0-100)	set on 0.
	Index values summarize the health state, range from less	Index value
	than 0 (0 indicates a health state equivalent to dead, negative	cannot be
	values a health state as worse than dead) to 1 (full health)	calculated if a
	Index values are calculated using the R package eq5d [6]:	dimension value
	eq5d::eq5d(scores = data %>% dplyr::select(MO = "eq5d_1", SC	is missing.
	= "eq5d_2", UA = "eq5d_3", PD = "eq5d_4", AD = "eq5d_5"),	
	country = "Sweden2022", version = "5L", type = "VT",	
	ignore.invalid = TRUE)	

Confidential Page 14 of 21

#### NAD metabolome

- Nicotinamide adenine dinucleotide total (NAD+ and NADH)
- Nicotinamide adenine dinucleotide oxidized (NAD+)
- Nicotinamide adenine dinucleotide reduced (NADH)
- NAD+/NADH ratio
- Nicotinamide adenine dinucleotide phosphate total (NADP+ and NADPH)
- Nicotinamide adenine dinucleotide phosphate oxidized (NADP+)
- Nicotinamide adenine dinucleotide phosphate reduced (NADPH)
- NADP+/NADPH ratio
- 1-methyl nicotinamide (Me-Nam)
- Nicotinic acid-adenine dinucleotide (NAAD)
- N1-methyl-2-pyridone-5-carboxamide (Me-2-PY)
- N-Methyl-4-pyridone-5-carboxamide
- Nicotinamide (Nam)
- Nicotinamide N-oxide (Nam N-oxide)
- Nicotinic acid riboside (NAR)
- Nicotinamide riboside (NR)
- Nicotinamide mononucleotide (NMN)
- Nicotinic acid (NA)

#### 5.2 Analysis methods

#### Primary endpoint analysis

The primary endpoint, the MDS-UPDRS changes from baseline to week 52 between the NR and placebo group, will be analyzed using Gaussian linear models for repeated measures (MMRM) with intervention, center, time (week 13, 26, 39, and 52), and intervention-by-time interaction as factors, and baseline MDS-UPDRS score as covariate. Centers with fewer than 20 patients are pooled into one center. The error terms are assumed to follow a multivariate normal distribution with unstructured covariance. Least square mean changes for both groups as well as the difference between the least squares treatment group means will be reported with 95% CIs and p-value testing the null hypothesis of no treatment effect.

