### 2.3 Sample Size

For sample size calculation we assume a common standard deviation of 16 points in the total MDS-UPDRS (parts I, II and III) and an overall type 1 error rate of 5%. Such a standard deviation was seen in Holden et al (2018). This estimate is further supported by a blinded sample size review performed on a blinded data export from August 23, 2024. A sample size of 162 participants per group gives an 80% power given a difference of 5 points in the total MDS-UPDRS at 52 weeks between the NR and the placebo group (324 in total). A difference of this magnitude was reported to be within the clinically meaningful range (see Wyman-Chick et al (2018)). Accounting for approx. 20% drop out, 200 participants per group (400 in total) are required.

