# 3 Statistical Principles

## 3.1 Confidence intervals and p-values

Unless specified otherwise, all tests will be performed two-sided on a significance level of 5%. Consequently, confidence intervals (CI) will be reported with 95% confidence level.

Confidential Page 11 of 21

<sup>1Includes: family history of neurological illness, smoking history, anamnestic months since first clinical PD symptoms, occurrence and duration of REM sleep behaviour disorder symptoms, occurrence and duration of loss of smell.

<sup>2 CRP, ALAT, ASAT, GT, bilirubin, ALP, creatinine, urea, RBC, Hb, WBC with differential, platelets, CK, FT4, TSH, B12, folic acid, homocysteine, methylmalonic acid, sodium, potassium.

<sup>3 PBMC analysis is discontinued for new patients enrolled after 16.04.23. Patients enrolled before 16.04.23 will complete PBMC as described.

<sup>4 If necessary to resupply.

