#### Secondary endpoints analyses

The analyses of continuous secondary endpoints with multiple measurement times, namely the MDS-UPDRS part I, II and III and the NMSS total and domain scores, are compared between the

Confidential Page 15 of 21

treatment groups by the MMRM model as described for the primary endpoint. The change in the mean Striatal Binding Ratio (SBR), in the total MOCA score and in the EQ-5D-5L index value are compared between the treatment groups by analysis of covariance (ANCOVA) with intervention and center as factors and baseline value as covariate. Least square mean changes for both groups as well as the difference between the least squares treatment group means will be reported with 95% CIs and p-value testing the null hypothesis of no treatment effect. The family-wise error rate across the key secondary endpoints, namely MDS-UPDRS part 1, 2 and 3, mean striatal binding ratio and NMSS total score, will be controlled by application of the Hochberg procedure. The key secondary endpoints are only tested for significance if the primary endpoint is statistically significant. The analyses of other secondary endpoints and safety parameters will have an exploratory character and will therefore not be adjusted for multiple testing.

The Hoehn and Yahr stage at 52 weeks will be compared between the treatment groups by ordinal regression with intervention, center and baseline stage as factors.

```
library(ordinal)
library(emmeans)
library(rstatix)
mod.sec <- clm(HoehnYahr w52 ~ HoehnYahr.BL + group + center,</pre>
                  link = 'logit', data = dataEndpoints)
emm.ord <- emmeans(mod.sec, ~ HoehnYahr w52 | group, mode = 'prob',
                   adjust = 'none') %>% as.data.frame()%>%
mutate(Prob = sprintf('%.3f (%.3f, %.3f)', prob, asymp.LCL, asymp.UCL)) %>%
dplyr::select(HoehnYahr.V10, RANDTRT, Prob) %>%
pivot wider(values from = Prob, names from = group)
comp <- pairs(emmeans(mod.sec, specs = 'group'))</pre>

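### The primary MMRM uses one baseline slope for all four visits; if the link with baseline weakens over the year, the week-52 contrast loses a little precision that a baseline-by-time term would recover

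*SAP*

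**What the plan says.** SAP Section 5.2 (Primary endpoint analysis) names every term of the model. The fixed effects are "intervention, center, time (week 13, 26, 39, and 52), and intervention-by-time interaction as factors", followed by "and baseline MDS-UPDRS score as covariate". For the residuals, "The error terms are assumed to follow a multivariate normal distribution with unstructured covariance". The only interaction with time is that of intervention, so baseline has one coefficient for all four visits. The quantity of interest is at one visit: "the MDS-UPDRS changes from baseline to week 52 between the NR and placebo group".

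The same section (Secondary endpoints analyses) compares MDS-UPDRS parts I, II and III and the NMSS between the "treatment groups by the MMRM model as described for the primary endpoint". Four of the five key secondary endpoints therefore inherit the single slope. The fifth, the striatal binding ratio, is analysed by ANCOVA. Table 3 (Section 2.7) schedules MDS-UPDRS at weeks 13, 26, 39 and 52, but NMSS only at weeks 26 and 52 after baseline.

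**The concern.** The model is flexible by visit in two respects (treatment effect and covariance) and rigid in a third (baseline adjustment). In a progressive disease the correlation between baseline and follow-up may fall as follow-up lengthens. A slope pooled over four visits would then be too steep for week 52, the only visit that counts for the primary test.

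At stake is a small amount of precision in the confirmatory contrast, which also decides whether the key secondary endpoints are tested at all. In large samples with complete data, visit-specific slopes cannot be less precise at week 52 than a common slope, so the restriction brings no compensating gain.

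**Working it through.** **1. The plan's own figure.** Section 2.3 gives difference 5, SD 16, 80% power and 162 per group; Section 3.1 makes tests two-sided at 5%. The normal approximation gives n = 2 × (1.960 + 0.842)² × 16² / 5² = 160.7, so 161 per group. With the t-test, power is 0.7983 at 161 and 0.8007 at 162. The stated 162 is reproduced. The calculation is a plain two-group comparison with no stated credit for baseline adjustment. The SAP does not say whether 16 is the SD of the score, the change or the adjusted residual.

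**2. Formula for the common slope.** Let b_j be the true slope on baseline at visit j and S the 4×4 residual covariance given baseline. With unstructured covariance, the single slope converges to

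b_c = Σ w_j b_j, with w = S⁻¹1 / (1′S⁻¹1).

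The week-52 residual variance becomes

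S_44 + (b_52 − b_c)² × Var(baseline),

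against S_44 with visit-specific slopes. The added term is never negative and is zero when the slopes are equal. Modelling change instead of score shifts every slope by −1 and leaves b_52 − b_c the same.

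**3. Four scenarios.** These inputs are assumptions, not SAP figures: correlation a × φ^(weeks apart/13), baseline SD 16, and later SDs either 16 or rising linearly to 18.

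| a, φ, SD | b_13 to b_52 | week-13 weight | b_c | S_44 | added | variance | SE |
|---|---|---|---|---|---|---|---|
| 0.90, 0.93, 16 | 0.837 to 0.673 | 0.57 | 0.793 | 140.0 | 3.7 | +2.6% | +1.3% |
| 0.90, 0.95, 16 | 0.855 to 0.733 | 0.54 | 0.821 | 118.4 | 2.0 | +1.7% | +0.8% |
| 0.85, 0.95, 16 | 0.808 to 0.692 | 0.46 | 0.769 | 133.3 | 1.5 | +1.1% | +0.6% |
| 0.90, 0.93, 16 to 18 | 0.863 to 0.757 | 0.62 | 0.841 | 177.1 | 1.8 | +1.0% | +0.5% |

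First row: b_c − b_52 = 0.120, and 0.120² × 256 = 3.7; 3.7/140.0 = 2.6%; √1.0264 − 1 = 1.3%. In patients, 400 × (1 − 1/1.0264) ≈ 10; the last row gives about 4.

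**4. Wider range (also assumed).**
- Score SD 16, decaying correlation, 10% measurement error: SE excess 2.6%, 1.9%, 1.1% and 0.35% for baseline-to-week-52 correlations of 0.5, 0.6, 0.7 and 0.8.
- No measurement error: 2.6% to 5.2%, the worst case tried.
- Constant correlation: visit weights 0.25 each, slopes equal, loss 0%.
- SD rising from 14 to 18: 0-1%.
- Random intercept and slope: 0% when the two are uncorrelated, otherwise 0.6-2.6%.

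**5. Simulation with dropout.** The set-up was 400 patients, about 18% dropout depending on the last score, 10% measurement error and a true difference of −5, with 400 runs per scenario (maximum likelihood, center omitted).

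| week-52 correlation | SE ratio, common / visit-specific | mean estimate, common | visit-specific |
|---|---|---|---|
| 0.5 | 1.031 | −4.87 | −4.93 |
| 0.7 | 1.014 | −5.00 | −5.01 |
| 0.8 | 1.005 | −4.95 | −4.95 |

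Power was 0.880 against 0.905 at correlation 0.5, and did not differ at 0.7 or 0.8.

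**6. Consequence for planned power.** If 16 is the SD of the score, the single-slope model at 162 per group still has power of at least 0.87 in the equal-SD scenarios of step 4. If 16 were already the residual SD after visit-specific adjustment, an SE excess of 1%, 3% or 5% would move normal-approximation power from 0.803 to 0.795, 0.780 or 0.764.

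**The case against.** The strongest reply is that nothing here is wrong. A single baseline slope is a valid, complete and unambiguous MMRM, and the loss depends on correlations and SDs the SAP does not report. Both points stand. Early-visit dominance is not general either: under constant correlation the four visits weigh equally. The effect is also small: 2.6% in variance is only 1.3% in SE.

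Four stronger readings are tempting, and the documents support none of them.

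- *The planned MMRM is worse than a week-52 ANCOVA.* With complete data the ANCOVA slope is the free one. With dropout, however, the MMRM also uses partial follow-up. Assuming 200 per group and 5% lost before each visit, the common-slope MMRM beats ANCOVA in week-52 completers in all four scenarios of the first table (per-patient variance 170 against 175, 143 against 148, 161 against 167, 212 against 221).
- *The wrong slope undermines the missing-at-random argument.* The simulation shows no material bias when dropout depends on the last score. Dropout driven by baseline was not examined, so nothing can be claimed for it. Sections 5.3 and 5.4 already plan a reference-based imputation sensitivity analysis.
- *Chance baseline imbalance is a further harm.* An imbalance of one standard error, 16 × √(2/200) = 1.6 points, would shift the contrast by 0.12-0.19 points in the four scenarios. That shift is the same b_c − b_52 term that produces the extra variance, and it averages to zero under randomisation.
- *The four-visit figures carry over to the secondary endpoints.* Nothing was computed for parts I-III or NMSS, and NMSS has only two post-baseline visits.

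What survives is that the restriction gains nothing at week 52 and costs almost nothing to remove.

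**Conclusion.** The point holds as a minor, conditional efficiency remark. The SAP fixes one baseline slope across four visits for a contrast that concerns only the last. If the link with baseline weakens over the year, the week-52 standard error is larger than it need be: by 0.5-1.3% in the four main scenarios, and by roughly 0-3% over a wider range, with a worst case near 5%. If the slopes are equal, the loss is exactly zero. All these sizes rest on assumed correlations, SDs and measurement error.

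A reader might infer that the primary test is biased or that the trial is underpowered. Neither follows: randomisation keeps the contrast essentially unbiased, and the stated 80% power is not shown to fail.

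**What to change.** Before unblinding, add a baseline MDS-UPDRS-by-time interaction to the fixed effects of the primary MMRM in Section 5.2. Add the matching baseline-by-time term to the MMRMs for MDS-UPDRS parts I, II and III and for NMSS, each using its own baseline score.

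The cost is 3 degrees of freedom for the primary model and for each of parts I-III (four visits), and 1 for NMSS (two visits), with about 400 patients planned. It needs no new data, visits or patients. The timing matters because a term added after unblinding could look data-driven.

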#### Secondary endpoints analyses

The analyses of continuous secondary endpoints with multiple measurement times, namely the MDS-UPDRS part I, II and III and the NMSS total and domain scores, are compared between the

Confidential Page 15 of 21

treatment groups by the MMRM model as described for the primary endpoint. The change in the mean Striatal Binding Ratio (SBR), in the total MOCA score and in the EQ-5D-5L index value are compared between the treatment groups by analysis of covariance (ANCOVA) with intervention and center as factors and baseline value as covariate. Least square mean changes for both groups as well as the difference between the least squares treatment group means will be reported with 95% CIs and p-value testing the null hypothesis of no treatment effect. The family-wise error rate across the key secondary endpoints, namely MDS-UPDRS part 1, 2 and 3, mean striatal binding ratio and NMSS total score, will be controlled by application of the Hochberg procedure. The key secondary endpoints are only tested for significance if the primary endpoint is statistically significant. The analyses of other secondary endpoints and safety parameters will have an exploratory character and will therefore not be adjusted for multiple testing.

The Hoehn and Yahr stage at 52 weeks will be compared between the treatment groups by ordinal regression with intervention, center and baseline stage as factors.

```
library(ordinal)
library(emmeans)
library(rstatix)
mod.sec <- clm(HoehnYahr w52 ~ HoehnYahr.BL + group + center,</pre>
                  link = 'logit', data = dataEndpoints)
emm.ord <- emmeans(mod.sec, ~ HoehnYahr w52 | group, mode = 'prob',
                   adjust = 'none') %>% as.data.frame()%>%
mutate(Prob = sprintf('%.3f (%.3f, %.3f)', prob, asymp.LCL, asymp.UCL)) %>%
dplyr::select(HoehnYahr.V10, RANDTRT, Prob) %>%
pivot wider(values from = Prob, names from = group)
comp <- pairs(emmeans(mod.sec, specs = 'group'))</pre>

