# Display probabilities and p-value of pairwise contrast
qflextable(emm.ord) %>%
set caption(paste0("Probabilities for the Hoehn & Yahr stage at 52 weeks in
the treatment groups (", p format(comp$p.value, digits = 3, add.p =
T),")"))
```

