#### **Major Protocol Deviations**

- 1. Enrolment of a participant not meeting inclusion/exclusion criteria (e.g., PD diagnosis >2 years, H&Y ≥3, no DAT confirmation, use of high-dose vitamin B3).
- 2. Informed consent not obtained prior to study procedures.
- 3. Incorrect randomization or failure to randomize per protocol.
- 4. Non-adherence to investigational product (IP) administration with < 90% compliance or not taking study medication for > 14 days consecutively, or not taking study medication within 3 days from the last visit.
- 5. Non-adherence to the standardized dopaminergic regimen (Regimens A–C, see study protocol) after baseline.
- 6. Missing primary efficacy endpoint assessment (MDS-UPDRS Total) at any visit.

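### The Hoehn and Yahr table averages predicted probabilities equally over baseline stages and centres, so the stage probabilities shown by arm do not describe the enrolled patients (a minor reporting error)

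*SAP*

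**What the plan says.** SAP section 5.2 (Secondary endpoints analyses) compares Hoehn and Yahr stage at week 52 by "ordinal regression with intervention, center and baseline stage as factors". The code has main effects only: "mod.sec <- clm(HoehnYahr w52 ~ HoehnYahr.BL + group + center". The probabilities come from "emm.ord <- emmeans(mod.sec, ~ HoehnYahr w52 | group, mode = 'prob", with no weights argument. The test comes from a separate call, "comp <- pairs(emmeans(mod.sec, specs = 'group". The table is captioned "Probabilities for the Hoehn & Yahr stage at 52 weeks in" the treatment groups, and the p-value of the contrast is placed in the caption. The columns hold a probability and its limits for each stage and arm. From the contrast, only the p-value is printed.

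Four other places bear on the point:
- Section 4.2 requires "Hoehn & Yahr Score < 3 at enrolment", so eligible patients can be at stage 0, 1 or 2.
- The appendix foresees enrolment outside the criteria ("PD diagnosis >2 years, H&Y ≥3, no DAT confirmation"), and its table keeps such patients in the full analysis set.
- Section 5.2 says, for the primary model, "Centers with fewer than 20 patients are pooled into one center".
- Table 1 lists this endpoint under other secondary, and section 5.2 treats that group as exploratory, without multiplicity adjustment.

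**The concern.** A reader will take a table captioned as stage probabilities in the treatment groups to describe the patients in those groups. With factors in the model and no weights, `emmeans` gives each factor level the same weight. A baseline stage with a handful of patients then counts as much as the commonest one, and a small centre as much as the largest. Week 52 stage depends strongly on baseline stage, so the displayed probabilities can sit well away from the trial's own stage counts. Nothing in the SAP names the reference population or standardises to the sample.

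This matters more because the probabilities are the only description of effect size in the planned output. The log odds ratio is computed in the contrast object but is not printed.

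**Working it through.** The SAP gives no figure for this table, no baseline stage distribution and no centre sizes. The mechanism can be checked exactly; its size can only be shown over stated assumptions.

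**1. Which average does the code compute?** Let p_k(s,c,g) be the predicted probability of stage k for baseline stage s, centre c and arm g.
- Equal weighting: P_k(g) = (1/(S·C)) Σ_s Σ_c p_k(s,c,g), with S stages and C centres.
- Sample weighting: P_k(g) = Σ_s Σ_c w_sc p_k(s,c,g), where w_sc is the share of patients in the cell.

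The SAP's call was run on a simulated proportional-odds model with the SAP's terms. It was fitted with `MASS::polr`, because the `ordinal` package was not available. Assumptions: n = 4000; baseline stages 1:2 at 25:75; six centres holding 35/20/15/12/10/8% of patients. Placebo results:

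| | Stage 1 | Stage 2 | Stage 3 |
|---|---|---|---|
| SAP call, no weights | 0.459 | 0.471 | 0.070 |
| Simple mean over all stage-by-centre cells | 0.459 | 0.471 | 0.070 |
| `weights = 'proportional'` | 0.321 | 0.594 | 0.085 |
| Standardised over patients | 0.321 | 0.594 | 0.085 |
| Raw proportions | 0.320 | 0.601 | 0.079 |

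The first two rows agree to all printed digits, so the weighting is equal. The error for stage 1 is 0.459 − 0.321 = 0.138, about 14 points. Proportional weighting recovers the raw figure.

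**2. How does the error depend on the mix (two levels)?** The same kind of model, computed analytically, gives for placebo stage 1:
- 50:50: 0.468 against 0.490, about 2 points, all of it from unequal centres.
- 25:75: 0.468 against 0.318, 15 points.
- 10:90, where one level is already thin: 0.468 against 0.214, about 25 points.

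A second set of assumptions takes P(stage ≥ 2 at week 52) as 8%, 35% and 95% for baseline stages 0, 1 and 2. With two levels, equal weighting gives (0.35 + 0.95)/2 = 0.650. The population figures for stages 0/1/2 are:
- 1/50/49%: 0.01×0.08 + 0.50×0.35 + 0.49×0.95 = 0.641, an error of about 1 point.
- 1/35/64%: 0.01×0.08 + 0.35×0.35 + 0.64×0.95 = 0.731, an error of about 8 points.
- 2/25/73%: 0.02×0.08 + 0.25×0.35 + 0.73×0.95 = 0.783, an error of about 13 points.

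**3. What does a sparse level do?**
- If stage 0 forms a level of its own, equal weighting gives (0.08 + 0.35 + 0.95)/3 = 0.460. Against the three mixes above, the error is 18, 27 and 32 points.
- With 1% of patients at baseline stage 3, that level gets weight 1/3. In the first model (25:74:1) the placebo probability of stage 3 becomes 0.31 instead of 0.09.

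**4. What happens to the difference between arms?** Apply a common odds ratio OR to the 8/35/95% inputs: q = OR·p/(1 − p + OR·p). At OR = 0.63, q is 0.052, 0.253 and 0.923, so the differences by baseline stage are 2.8, 9.7 and 2.7 points.

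| Mix (stages 0/1/2) | OR | Population-weighted | Three equal levels | Two equal levels |
|---|---|---|---|---|
| 1/35/64% | 0.63 | 5.2 | 5.1 | 6.2 |
| 1/35/64% | 0.75 | 3.2 | 3.2 | 3.9 |
| 2/25/73% | 0.50 | 6.8 | 7.4 | 9.2 |

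The last row holds the largest shift over the three mixes and odds ratios of 0.50 to 0.75: 9.16 − 6.83 = 2.3 points. In the simulation of step 1, the stage 1 difference (NR minus placebo) is 0.520 − 0.459 = 0.061 unweighted and 0.384 − 0.321 = 0.063 weighted. The analytic model with 1% at stage 3 moves single-stage differences a little more: stage 2 goes from −0.028 to 0.000.

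**5. What happens to the test?** The simulated contrast is −0.468 (SE 0.0756) under both weightings. The model has no interaction with treatment, so the averaging weights cancel.

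**The case against.** The strongest case is that this concerns display only. Both arms are averaged over the same grid, so the comparison is balanced. Equal-weight marginal means are a recognised convention, and the SAP reports least squares means elsewhere. The odds ratio and p-value are untouched, and no confirmatory claim rests on the endpoint. All of that stands, and it limits the severity.

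The size is also open to challenge, and rightly. A reader might infer that the table will be wrong by 18 to 32 points. The documents do not support that: it needs a separate stage 0 level, and nothing in the SAP shows that such a patient was enrolled. Stage 0 means asymptomatic, and entry requires a clinical diagnosis, although the stage criterion alone does not bar it. Nor can one infer that the treatment effect is distorted to that degree; the large figures are levels that shift together in both arms.

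The centre part is weak. Unequal centres alone moved the figures by about 2 points, and the pooling rule, if it carries over from the primary model, would remove very small centres.

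The code also reads like a template: it selects `HoehnYahr.V10` and `RANDTRT`, although the model uses a week 52 variable and `group`. An absent argument may therefore not be a deliberate choice. Even so, code run as written would give the equal-weight table under a caption that does not say so. Treating baseline stage as numeric would not help: with two observed values the output was the same to within rounding, and with more values it is held at its mean by default, which does not represent the sample either.

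**Conclusion.** The point holds as a minor reporting error. The displayed stage probabilities are equal-weight averages over baseline stages and centres, not probabilities for the enrolled patients. With two baseline levels, the error in the level is about 1 to 2 points near balance and about 13 to 15 points at roughly 25:75; it is larger only if a level is sparse. The difference between arms moves by at most about 2 points under the 8/35/95% inputs, and by nearly 3 points for one stage in the example with a stage 3 patient. The common odds ratio and the p-value do not change.

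These sizes rest on assumed baseline mixes, centre shares and transition probabilities, because the SAP gives none. The mechanism rests only on baseline stage and centre being factors, as the SAP states. Correcting it is worthwhile because the table could visibly disagree with the trial's own stage counts, and because choosing the weighting now avoids a choice after unblinding.

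**What to change.** - Add `weights = 'proportional'` to the probability call, or standardise the predictions over the baseline stages and centres of the analysed patients. Name that reference population in the caption.
- Compute the limits of the probabilities on the logit scale or by bootstrap. The limits the code takes are symmetric on the probability scale and could fall below 0 for a rare stage; this follows from their form and was not tested here.
- Print the common odds ratio with its 95% CI, from the existing contrast, beside the p-value.

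The cost is one argument, a caption edit and a few lines of output code. The variable names in the same block need aligning anyway. No data, design or protocol change is needed.
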